4.7.4 Additional safety assessments

4.7.4.1 Laboratory variables and vital signs

The following laboratory variables and vital signs will be converted into standard international units and analyzed from screening to week 16 per the schedule of events. Analysis will distinguish

between early end of treatment and week 16 end of treatment. Glucose values will be analyzed using conventional units.

- Hematology:
 - Red blood cells and platelets: erythrocytes, platelet count, leukocytes, hemoglobin, hematocrit
- Clinical chemistry:
 - Metabolism: lipase, amylase
 - Electrolytes: sodium, potassium
 - Renal function: creatinine, uric acid
 - Liver function: alanine aminotransferase, aspartate aminotransferase, alkaline phosphatase, total bilirubin (if >ULN , then the direct and indirect subfractions must be measured)
- Calcitonin
- Urinalysis:
 - Urinalysis for quantitative analysis: pH, ketones, leukocytes, blood/hemoglobin, protein and glucose
- Vital signs: pulse rate, systolic and diastolic blood pressure, weight

Specified in the study protocol, all clinical safety laboratory assessments will be performed by a central laboratory. Additional tests may be performed at a local or central laboratory at any time during the study as determined necessary by the investigator or required by local regulations. If they are used to evaluate an AE (diagnostic, follow-up, outcome), the results must be entered into the eCRF. A urine pregnancy test will be performed at each schedule of event timepoint and treated as an AESI and not reported in the laboratory analysis tables.

Quantitative analyses

Descriptive statistics will be used for results and changes from baseline will be provided for each planned visit, during the on-treatment period. Laboratory values below the lower limit of quantification (LLOQ) will be set to one half of the LLOQ.

4.7.4.2 Product complaints

Any defect in the IMP device must be reported as soon as possible by the investigator to the monitoring team, who will complete a product complaint form within the required timelines.

Appropriate information (eg, samples, labels, or documents like pictures or photocopies) related to product identification and to the potential deficiencies may need to be gathered. The investigator will assess whether the quality issue must be reported in association with an AE or SAE.

All product complaint summaries during the on-treatment period (see [Section 4.1](#)) will be generated using the safety set and will include the number (%) of participants experiencing at least one event, the number of events, and the event rate per participant-year.

The event rate per participant-year will be defined as the number of events divided by the cumulative duration of all participants' exposure expressed in years.

The overview of product complaints with the details below will be generated:

- Any product complaint
- Any product complaint related to AEs

In addition, the analysis below will be conducted.

- Any product complaint categorized by type of complaint
- AE(s) leading to product complaints by primary SOC and PT

4.8 OTHER ANALYSES

4.8.1 Descriptive Analyses

Other summary descriptive analyses will be provided based upon the efficacy assessments. This includes a summary descriptive analysis of TIR, TAR, TBR, fasting plasma glucose, and two analyses based on fasting self-monitoring plasma glucose value (SMPG) taken in the mornings 3-4 times per day, 3 days before visit to determine titration. This information is provided from the eDiary. The analyses for fasting SMPG will be based on data from week -2 to week 16 showing a descriptive analysis of both lowest and average SMPG of each.

4.8.2 Biomarker analyses

β -cell biomarker analyses fall outside this SAP. β -cell markers (glucose, insulin, and C-peptide) will be collected at baseline only during the MMTT at specific timepoints during Visit 3.1. These values will be utilized to model β -cell function by an external clinician once the trial is completed and the data are available.

4.9 INTERIM ANALYSES

No interim analysis is planned.

5 SUPPORTING DOCUMENTATION

5.1 APPENDIX 1 LIST OF ABBREVIATIONS

ADA:	American Diabetes Association
AE:	adverse event
AESI:	adverse events of special interest
AUC _{0-4h} :	area under the concentration versus time curve from time 0 to 4 hours
CGM:	continuous glucose monitoring
CI:	confidence interval
CV:	coefficient of variation
DM-SAT:	Diabetes Medication Satisfaction Tool
DPP-4i:	dipeptidyl peptidase-4 inhibitor
eCRF:	electronic case report form
GLP-1RA:	glucagon-like peptide 1 receptor agonist
GMI:	Glucose Management Indicator
HbA1c:	glycated hemoglobin
HLGT:	high level group term
HLT:	high level term
HRQoL:	health related quality of life
ICF:	informed consent form
IMP:	investigational medicinal product
LLOQ:	lower limit of quantification
LLT:	lower-level term
MCAR:	missing completely at random
MedDRA:	medical dictionary for regulatory activities
MMTT:	mixed-meal tolerance test
MODD:	mean of daily difference
OAD:	oral antidiabetic drug
OC:	observed cases
PPG:	postprandial glucose
PRO:	patient reported outcome
PT:	preferred term
SAE:	serious adverse event
SAP:	statistical analysis plan
SD:	standard deviation
SMPG:	self-measured plasma glucose
SOC:	system organ class
SU:	sulfonylurea
T2DM:	type 2 diabetes mellitus
TAR:	time above range, time above range
TBR:	time below range
TE:	treatment emergent
TEAE:	treatment-emergent adverse event

TIR:	time in range
TITR:	Time in Tight Range
T _{max} :	time to reach maximum concentration
ULN:	upper limit of normal
WHO-DD:	World Health Organization-drug dictionary

5.2 APPENDIX 2 CHANGES TO PROTOCOL-PLANNED ANALYSES

There are no changes to protocol-planned analyses.

5.3 APPENDIX 3 DEMOGRAPHICS AND BASELINE CHARACTERISTICS, PRIOR OR CONCOMITANT MEDICATIONS

5.3.1 Protocol deviations

Significant protocol deviations, including drug dispensing irregularities, will be summarized in the enrolled analysis set. Protocol deviations due to the COVID-19 pandemic will be categorized as such. Protocol deviations will come from the clinical trial management system and will be categorized according to the rules document for protocol deviations.

A listing of participants with at least one significant protocol deviation will be provided with comprehensive information related to each deviation identified.

5.3.2 Demographics and baseline characteristics

Treatment adherence, demographics, and baseline characteristics will be summarized in descriptive tables. Continuous data will be summarized using the number of observations available, mean, SD, quartile ranges, minimum, median, and maximum. Categorical data will be summarized using count and percentage.

Baseline safety and efficacy parameters will be presented along with the safety and efficacy summaries.

The following demographics and baseline characteristics will be summarized:

- age in years as continuous variable and in categories of $65 \leq$ and > 65
- gender (Male, Female)
- race: White, Black or African American, Asian (will subgroup Asian with Chinese, Japanese, Asian Indian, Korean, Other Asian Origin, Multiple Asian Origin, Asian Origin Not Reported, Asian Origin Unknown), Other, Multiple, Not Reported, Unknown.
- ethnicity (Hispanic or Latino, not Hispanic or Latino, Not Reported, Unknown, Other Ethnicity)
- weight (kg)

- height (cm)
- BMI in kg/m² as documented in eCRF and in categories BMI ≤ 30 (kg/m²) and BMI > 30 (kg/m²)
- OAD status (OAD with GLP-1RA or OAD without GLP-1RA)

5.3.3 Medical or surgical history

Medical (or surgical) history includes all the relevant medical (or surgical) history during the lifetime of the participant. Medical and surgical history will be coded to a LLT, PT, HLT, HLGT, and associated primary SOC using the MedDRA version currently in effect at Sanofi at the time of database lock.

Specific disease history, including gestational diabetes, will be reported in the summary.

Comorbidities will be summarized separately. Comorbid disease will be summarized from eCRF pages on the physical exam page completed by investigators based on participant report. Body system will be examined as assessment and defined as normal, abnormal, or not done.

Medical and surgical history will be summarized for enrolled participants and by SOC and PT, sorted by internationally agreed order of SOC and by the decreasing frequency of PT within SOC.

5.3.4 Disease characteristics at baseline

The following baseline disease characteristics will be summarized (see [Section 5.4.1](#) for calculation details):

- HbA1c background %
- Renal Function (measured in creatinine and uric acid)
- Background medication.
- Duration of diabetes
- Age at onset T2DM

Any technical details related to computation, dates, and imputations for missing dates are described in [Section 5.4.2](#).

Continuous data will be summarized using the number of observations, mean, standard deviation (SD), median, minimum, and maximum for enrolled participants. Categorical and ordinal data will be summarized using the number and percentage of enrolled participants.

5.3.5 Prior and concomitant medication

All medications will be coded using the World Health Organization-Drug Dictionary (WHO-DD) using the version currently in effect at Sanofi at the time of database lock.

- Prior medications are those the participant used prior to first IMP administration. Prior medications can be discontinued before first administration or can be ongoing during treatment period.
- Concomitant medications are any interventions received by the participant concomitantly to the IMP during the on-treatment period/from the first administration of IMP to the last IMP administration + 1 day.
- Post-treatment medications are those the participant took in the timeframe spanning the last IMP administration +2 days (week 16) up to the end of the study (Week 18).
- A given medication can be classified as a prior medication and/or as a concomitant medication and/or as a post-treatment medication. If it cannot be determined whether a given medication was taken prior or concomitantly or post, it will be considered as prior, concomitant, and post-treatment medication.

The prior and concomitant and post-treatment medications will be summarized for the enrolled set, by anatomic and therapeutic level. The summaries will be sorted by decreasing frequency of anatomic category (ATC) based on incidence. In case of equal frequency, alphabetical order will be used. Participants will be counted once each ATC category (anatomic or therapeutic) linked to the medications.

Use of all concomitant medications will be recorded in the participant's eCRF. This includes all prescription drugs, herbal products, vitamins, minerals, and OTC medications. Any changes in concomitant medications will also be recorded in the participant's eCRF.

5.4 APPENDIX 4 DATA HANDLING CONVENTIONS

5.4.1 Demographic formulas

Age (years) = (Year of informed consent date – Year of birth)

5.4.2 Disease characteristics formulas

Duration of diabetes (years) = (Date of informed consent - Date of diagnosis of diabetes + 1)/365.25

Age at diagnosis of diabetes (years) = Year of diagnosis of diabetes – Year of birth

5.4.3 Reference dates

For efficacy analyses, Day 1 reference date is a participant's enrollment date. For safety assessments, the Day 1 reference date is a participant's first treatment date.

5.4.4 Missing Data

For categorical variables, participants with missing data are not included in calculations of percentages unless otherwise specified. When relevant, the number of participants with missing data is presented.

Medication missing/partial dates

No imputation of medication start/end dates or times will be performed. If a medication date or time is missing or partially missing and it cannot be determined whether it was taken prior or concomitantly, it will be considered a prior and a concomitant medication.

Adverse events and Hypoglycemic events with missing or partial date/time of onset

Missing or partial adverse event onset dates and times will be imputed so that if the partial adverse event onset date/time information does not indicate that the adverse event started prior to treatment, the adverse event will be classified as treatment emergent. These data imputations are for categorization purpose only and will not be used in listings. No imputation is planned for date/time of adverse event resolution.

Missing date and time of first IMP administration

When the date and time of the first IMP administration is missing, all adverse events that occurred on or after first dose day defined by the eCRF should be considered as treatment-emergent adverse events.

The exposure duration should be kept as missing.

Missing severity of adverse events

If the severity is missing for 1 of the treatment-emergent occurrences of an adverse event within data collection per MedDRA PT, the maximal severity on the remaining occurrences will be considered. If the severity is missing for all the occurrences, a “missing” category will be added in the summary table.

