4.7.2 Adverse events

All AEs will be collected from the signing of the ICF until the follow-up visit.

General common rules for adverse events

All adverse events (AEs) will be coded to a lower-level term (LLT), preferred term (PT), high-level term (HLT), high-level group term (HLGT), and associated primary system organ class (SOC) using the Medical Dictionary for Regulatory Activities (MedDRA) version currently in effect at Sanofi at the time of database lock.

The AEs (which are recorded on the AE eCRF page, including hypoglycemia events qualifying as AEs) will be categorized as:

- Pre-treatment AEs: AEs that developed, worsened or became serious during the pre-treatment period, defined as the time from the signed informed consent date up to the first administration of the IMP.
- Treatment-emergent adverse events (TEAE)s: AEs that developed, worsened or became serious during the treatment-emergent period defined as the time from the first administration of the IMP (on Day 1) to the last administration of the IMP + 3 days.
- Post-treatment AEs: AEs that developed, worsened or became serious during the post-treatment period defined as the time starting 1 day after the end of the TEAE period up to the end of the study follow-up (2 weeks after the end of treatment period)

Similarly, the deaths will be analyzed in the pre-treatment, treatment-emergent and post-treatment periods.

Pre-treatment safety data will be analyzed using the Screening Analysis Set. Treatment-emergent and post-treatment safety data will be analyzed using the Safety Analysis Set.

The primary focus of AE reporting will be on TEAEs, and AESIs. Pre-treatment and post-treatment AEs will be described separately.

An AE with incomplete or missing date/time of onset (occurrence, worsening or becoming serious) will be classified as a TEAE unless there is definitive information to determine it is a pre-treatment or a post-treatment AE.

If the assessment of the relationship to IMP is missing for an AE, the AE will be assumed to be related to IMP within summary tables. If the severity is missing for one of the treatment-emergent occurrences of an AE, the severity will be imputed with the maximal severity of the other occurrences within the PT. If the severity is missing for all the occurrences, the severity will be left as missing.

Multiple occurrences of the same event in the same participant will be counted only once in the tables within a treatment phase.

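### SAP 5.4.4 and 4.7.2 conflict on events with an incomplete onset date/time: only 4.7.2 lets an event known to have started in follow-up stay out of the treatment-emergent tables

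*SAP*

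**What the plan says.** **AE periods (SAP 4.7.2).** The treatment-emergent period runs from the first dose "to the last administration of the IMP + 3 days". The post-treatment period is "the time starting 1 day after the end of the TEAE period up to the end of the study follow-up", which ends 2 weeks after the end of treatment. Table 6 plans separate post-treatment AE and SAE summaries.

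**Incomplete onset, first rule (SAP 4.7.2).** An AE with an incomplete or missing onset date/time "will be classified as a TEAE unless there is definitive information to determine it is a pre-treatment or a post-treatment AE".

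**Incomplete onset, second rule (SAP 5.4.4, Appendix 4).** Under the heading "Adverse events and Hypoglycemic events with missing or partial date/time of onset", the imputation is set so that if the partial information "does not indicate that the adverse event started prior to treatment, the adverse event will be classified as treatment emergent". The section adds: "These data imputations are for categorization purpose only and will not be used in listings".

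**Hypoglycemia (SAP 4.7.3).** The treatment-emergent period ends 1 day after the last injection, and a post-treatment period is defined separately. The section has no rule for a missing or partial onset.

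**Medications.** For a drug whose timing cannot be determined, 5.4.4 says "it will be considered a prior and a concomitant medication", while 5.3.5 says "it will be considered as prior, concomitant, and post-treatment medication".

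**The concern.** Two sections of one SAP give different rules for the same data problem, and neither refers to the other. The rule in 5.4.4 has one way out of the treatment-emergent class (evidence of onset before treatment). The rule in 4.7.2 has two (before or after). Two programmers working from different sections could therefore produce different TEAE and post-treatment tables from identical data.

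The trigger is not limited to badly recorded dates. Both rules refer to date and time together, so on its wording 5.4.4 also catches an event with a complete calendar date and no clock time. If that date lies in follow-up, 5.4.4 classifies the event against the period definitions in 4.7.2. The event enters the TEAE tables (and the serious TEAE table, if serious) and drops out of the post-treatment tables. Follow-up is also when some participants will have moved to another antihyperglycemic therapy after Visit 7 (protocol 3.1.2), so it matters that these events stay in their own period.

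**Working it through.** The documents state no figure to reproduce, and the point depends on no power or sample-size input. The check sets the rules side by side.

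**Inputs.** Let L be the date of the last dose.
- AE treatment-emergent period: first dose to L+3 (SAP 4.7.2).
- AE post-treatment period: starts 1 day later, at L+4. With Visit 8 on Day 126 and Visit 7 on Day 112 (schedule of events), follow-up ends at L + (126 − 112) = L+14. The period lasts 14 − 4 + 1 = 11 days.
- Hypoglycemia treatment-emergent period: first dose to L+1 (SAP 4.7.3).

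**AEs under each rule**

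| What is known about onset | 4.7.2 | 5.4.4, literal | Agree? |
|---|---|---|---|
| Shown to be before first dose | Pre-treatment | Pre-treatment | Yes |
| Date wholly missing | TEAE | TEAE | Yes |
| Month/year only, compatible with on-treatment onset | TEAE | TEAE | Yes |
| Month/year only, month later than that of L+3 | Post-treatment | TEAE | **No** |
| Full date from L+4 on, time missing | Post-treatment | TEAE | **No** |

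An invented example: the last dose is on 20 March, so the treatment-emergent period ends on 23 March and follow-up ends on 3 April. An AE dated 30 March (L+10) with no clock time is post-treatment under 4.7.2 and a TEAE under 5.4.4. An AE dated only April splits the same way. An AE dated only March is a TEAE under both rules.

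The rules therefore differ only for events that the available date parts definitely place after L+3.

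**Hypoglycemia.** The AE rules of 4.7.2 reach only hypoglycemia that qualifies as an AE. For the rest, 5.4.4 is the only missing-date rule, and it applies through its heading alone, because the rule sentence names only adverse events. If it does apply, it again allows no post-treatment class, although 4.7.3 defines one.

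**A gap found on the way.** Section 4.7.3 starts post-treatment hypoglycemia 1 day after the end of the TEAE period. Taking that term as 4.7.2 defines it, the start is (L+3) + 1 = L+4. Treatment-emergent hypoglycemia ends at L+1, so L+2 and L+3 appear to belong to neither period. If the term was meant as the hypoglycemia period, the start would be L+2 and there is no gap. The text does not settle which was meant.

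**Medications.** Both rules classify inclusively. Section 5.4.4 assigns two classes and 5.3.5 assigns three. The post-treatment class is the only difference.

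**The case against.** The strongest reply is that 4.7.2 already contains the right rule, under its general rules for AEs, and a sensible programmer would follow it. This stands in part. A reader might infer from 5.4.4 that follow-up events will be counted as treatment-emergent. The documents do not support that as a statement of fact, because it happens only if 5.4.4 is applied over 4.7.2. What they do support is an unresolved conflict.

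A second reply is that counting doubtful events as treatment-emergent is deliberately conservative. It is, but both rules already do so wherever the date is in doubt. The extra reach of 5.4.4 covers only events that are not in doubt.

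Third, few records should be affected. The protocol collects the AE time of onset (6.3.5.5) and the date and time of hypoglycemia (6.3.2), follow-up is short, and about 100 participants are planned. Safety is descriptive with no testing (SAP 4.7), and listings do not use the imputation. All of this stands and limits the importance of the point.

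Two stronger inferences should be resisted:
- **That the hypoglycemia rate would gain events after person-time has stopped.** The formula in 4.7.3 runs time to the event date for a participant with an event, so a reclassified follow-up event may extend person-time as well. Where time stops at an earlier event, later on-treatment events fall outside it too. That is a property of the formula and does not come from 5.4.4.
- **That a percentage inflation of TEAEs can be given.** No document gives the share of follow-up events with incomplete onset, or how many of those are decisively dated. The AE tables also count participants, with repeat occurrences of an event counted once per treatment phase, so one more event need not change an incidence.

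**Conclusion.** The conflict is real, and nothing in the SAP resolves it. Applied literally, 5.4.4 misclassifies events that the recorded date parts definitely place in follow-up. It changes nothing where the date is absent or not decisive. For AEs the conflict with 4.7.2 is direct. For hypoglycemia that does not qualify as an AE, the fault is that the only available rule leaves no room for the post-treatment period defined in 4.7.3, and it is unclear whether that rule applies at all.

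The size cannot be derived from the documents. It is expected to be small, limited to descriptive safety tables, with no effect on the primary endpoint or any efficacy analysis. The conclusion assumes that a known date without a clock time counts as a partial date/time, as the wording of 5.4.4 implies. If it did not, only events with a partial calendar date would be affected. Severity: minor. The medication mismatch is secondary.

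**What to change.** 1. Replace the classification sentence in SAP 5.4.4 with the 4.7.2 rule: an event with a missing or partial onset is treatment-emergent unless the available date parts show onset before the first dose or after the end of the relevant treatment-emergent period. State those ends: last dose +3 days for AEs, last dose +1 day for hypoglycemia.
2. Add that an event with a known date and a missing time is classified by its date.
3. State in the rule itself, and not only in the heading, that it applies to hypoglycemic events, and refer to it from 4.7.3.
4. Reconcile the start of the post-treatment hypoglycemia period in 4.7.3 with the end of its treatment-emergent period, so that days +2 and +3 after the last dose belong to one of them.
5. Make the undated-medication rule in 5.4.4 match 5.3.5 (prior, concomitant and post-treatment).

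The cost is a few sentences in the SAP and one condition in the period derivation, set with the appropriate end for each event type. No new data are needed.
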